1.0 PROTOCOL SUMMARY

Protocol Number	CXL-005, Revision 04.1
Title	Collagen Cross-Linking with Ultraviolet-A in Asymmetric Corneas
Sponsor	CXLUSA, LLC
Regulatory Status	Phase 2 investigational new drug study
Objectives	Assess changes in visual acuity and corneal symmetry after corneal collagen cross-linking (CXL) of asymmetric corneas.
Study Design	Prospective, randomized, controlled, open label, multicenter trial
Study Population	
A total of 3,000 males and females \geq 8 years old.
 
Inclusion Criteria A diagnosis of at least one of the following conditions:
 
1. Keratoconus2. Forme fruste keratoconus3. Post-LASIK ectasia4. Pellucid marginal degeneration5. Forme fruste pellucid marginal degeneration6. Diurnal fluctuation post-radial keratotomy7. Terrien's marginal degeneration 
Exclusion Criteria
 
1. Corneal thickness $<$ 375 microns measured by ultrasound or Pentacam.2. Contraindications or hypersensitivities to any study medications or their components.3. Pregnancy or breastfeeding.4. Any history of herpes simplex corneal disease in an eye to be treated.5. Nystagmus or any other condition that would, in the judgement of the investigator, prevent a steady gaze during the treatment.6. Inability to cooperate with diagnostic tests.7. Enrollment in another ophthalmic clinical trial.
Number of Centers	21
Investigational Product	CXLO Corneal Strengthening Solution; ultraviolet-A illuminator.
Study Procedures	
Pre-Procedure Screening Subjects will be instructed to remove contact lenses prior to screening – 2 weeks prior for rigid/gas permeable contact lenses and 3 days prior for soft or scleral lenses – unless subject has no suitable vision correction option. Mandatory screening procedures include medical, prior ophthalmic surgery, and contact lens history, refractive assessments for manifest refraction, uncorrected visual


Study Procedures (cont'd)
	
acuity (UCVA), corrected distance visual acuity (CDVA), corneal thickness (ultrasound pachymetry or other scanning device such as Pentacam), Pentacam corneal tomography, intraocular pressure (IOP), slit lamp examination, and dilated fundus exam.
 
Optional screening procedures include quality of life and/or comfort survey questions such as VFQ-25, ophthalmic assessments including corneal wavefront measurement, optical coherence tomography (OCT), Brillouin microscopy, iTrace wavefront aberrometry/topography, Orbscan corneal topography, tomography, contrast sensitivity testing, or other non-invasive diagnostic tools that may be available to an investigator, and previous ophthalmic history such as old eyeglass prescriptions and topographic maps.
 
When eligibility has been established using the inclusion/exclusion criteria, the patient will be enrolled.
 
Randomization Randomization will be stratified by indication and by investigational site among 3 UVA illumination groups consisting of:
 
Group 1: 4 mW/cm² cycled On/Off at 15 second intervals for 20 minutes (total UVA corneal surface dose of 2.4 J/cm²), or Group 2: 6 mW/cm² cycled On/Off at 15 second intervals for 20 minutes (total UVA corneal surface dose of 3.6 J/cm²), or Group 3: 4 mW/cm² cycled On/Off at 15 second intervals for 30 minutes (total UVA corneal surface dose of 3.6 J/cm²).

	
Day of Cross-Linking Procedure One or both eligible eyes may be treated on the same day, or on different days.
 
CXL Procedure
 
A. Instill anesthetic eye drops.B. Insert lid speculum in each eye undergoing treatment.C. Use a sterile ophthalmic sponge hydrated with saline or anesthetic drops to gently swab the surface of the cornea to remove mucus and any other debris and to enhance riboflavin penetration into the cornea. The epithelium is not to be removed, as treatment with an intact epithelium has the potential to halt progression of the disease while reducing post-procedure pain, complications related to


Study Procedures (cont'd)
	
epithelial debridement, and promoting faster vision recovery to baseline CDVA.
 
D. Apply a CXLO round loading sponge to the surface of the cornea to serve as a reservoir for CXLO Corneal Strengthening Solution.
 
E. Saturate the sponge with several drops of CXLO Corneal Strengthening Solution. Instill 1-2 drops of CXLO solution every 1-3 minutes for 10-90 minutes (this range is required as different corneas load at different rates and the surgeon will visually confirm sufficient stromal loading later in the procedure). Topical anesthetic drops may be used infrequently as needed (generally every 10 -15 minutes) to maintain patient comfort.
 
E. After 10-20 minutes of saturation, remove the lid speculum. Examine the eye using a slit lamp or a slit light to confirm uniform saturation of the cornea, referencing a “flip chart” of slit-lamp images, a copy of which is provided in Appendix 1. If the cornea is not adequately saturated, repeat the CXLO solution application instructions above, and re-assess corneal saturation via slit-lamp or slit light examination every 5-10 minutes until adequate, uniform corneal saturation is confirmed.
 
F. After confirming adequate stromal saturation, irrigate the corneal epithelium with artificial tears for approximately 30 seconds prior to UVA illumination to avoid the “sunscreen” effect of riboflavin in the epithelium.
 
G. Place the lid speculum(s) prior to UV light application.
 
H. Apply artificial tears every 30 to 60 seconds during UVA light application to avoid corneal drying. These artificial tear solutions may be stored overnight at room pressure under different atmospheric oxygen levels to test the effects of dissolved oxygen variations due to storage and altitude on cross-linking.
 
I. The total cumulative UVA dose will not exceed 3.6 Joules/cm². UV Irradiance will not exceed 6mW/cm² and the UVA light will illuminate a 12 mm diameter area on one or both corneas for 10-30 minutes. The irradiance and duration of UV exposure will be recorded.
 
J. After completion of the procedure:
 
1. The lid speculum is removed.2. Polytrim™ (or Floraquinolone or other appropriate broad spectrum antibiotic if the subject is hypersensitive) and anti-inflammatory drops are instilled. These may include Ciprofloxacin or Vigamox (or similar) and a nonsteroidal such as Voltaren, Acular or Xibrom. A topical steroid may also be instilled.
---	--

Clinical Parameters	
The following clinical parameters will be evaluated:
 
1. Corrected distance visual acuity2. Uncorrected distance visual acuity3. Slit lamp assessment4. Corneal topography/tomography5. Manifest refraction6. Pachymetry7. Intraocular pressure (IOP)8. Maximum corneal curvature (K_{max}) 
A schedule of assessment procedures is provided in Appendix 2.

Efficacy Endpoints	
Primary: Change in corrected distance visual acuity (CDVA) at 6 months, compared to baseline.
 
Secondary: Change at 6 months as compared to baseline in:
 
1. Uncorrected distance visual acuity2. K_{Max}
Statistical Methods	
Change from baseline will be calculated as follow-up visit – baseline. The baseline visit will be defined as Visit 1 (Pre-procedure visit). In general, continuous variables will be analyzed with two-sample t-tests for changes from baseline in normally distributed variables. For non-parametric data sets, Wilcoxon Signed Rank tests will be utilized. Patient demographics will be summarized using descriptive statistics (means, medians, standard deviations, etc.).
 
Subject demographic characteristics and background variables will be summarized. Treatment differences with respect to baseline characteristics will be discussed in the final study report and assessed.
 
All subjects enrolled in the study will be included as part of the safety analysis. All eyes treated (single or both eyes of an individual subject) will be included in the analysis of safety and efficacy.
 
To determine efficacy, standard statistical methods such as p value analyses of continuous variables will be used along with newer artificial intelligence algorithms such as Logitboost or Random Forest to detect groupings and correlations of various outcome variables ¹. Large data sets will be analyzed and in these analyses stratification by UVA irradiance and total dose, age, diagnosis, severity of disease, gender, tomography,

Statistical Methods (cont'd)	topography metrics and other such criteria will be used to answer key questions related to the science and effects of treatments. Reference: Statistical Learning for Biomedical Data JD Malley, KG Malley, S Pajevic Cambridge University Press, 2011)
---	---

TABLE OF CONTENTS

1.0	PROTOCOL SUMMARY	2
2.0	BACKGROUND AND INTRODUCTION	10
2.1	DESCRIPTION OF INDICATION FOR USE	10

12.0 REFERENCES30
APPENDIX 1: FLIP CHART OF RIBOFLAVIN CORNEAL LOADING33
APPENDIX 2: SCHEDULE OF ASSESSMENTS62
APPENDIX 3: UVA LIGHT CALIBRATION, CENTERING, AND APPLICATION INSTRUCTIONS63

2.0 BACKGROUND AND INTRODUCTION

Asymmetric corneas involved in this study are those caused by a number of “orphan” diseases that markedly impair vision due to progressive corneal thinning, steepening, and/or irregular astigmatism. These diseases include keratoconus, forme fruste keratoconus, post-LASIK ectasia, pellucid marginal degeneration, forme fruste pellucid marginal degeneration, diurnal fluctuation post-radial keratotomy, and Terrien’s marginal degeneration.

Current non-surgical treatment alternatives include soft or rigid contact lenses or spectacles. However, as the disease progresses, these treatment modalities may not provide functional vision. Implantable intracorneal ring segments have been shown to improve visual acuity, but they do not affect the underlying disease and are associated with several possible complications. As a result, a significant number of these patients have had no treatment alternatives other than corneal transplantation.

Corneal collagen cross-linking has been shown to halt the progression of keratoconus (Raiskup-Wolf et. al., 2008; Wittig-Silva et. al., 2008; Coskunseven et. al., 2009, Grewel et. al., 2009; Vinciguerra et. al., 2009, Agrawal 2009, Kymionis et. al., 2009; Caporossi et. al., 2010; Greenstein et. al., 2011; Mazzotta et. al., 2012; Pinelli and Marzouky 2009; Stojanovic et. al., 2012; Rubinfeld et. al., 2013), as well as post-LASIK ectasia (Kymionis et. al., 2009, Greenstein et. al., 2011, Hovakimyan et. al., 2012), pellucid marginal degeneration (Spadea 2010), diurnal fluctuation post-radial keratotomy (Elbaz et.al 2014), and Terrien’s marginal degeneration (Hafezi 2014).

The recent approval of the Avedro, Inc. system for corneal collagen cross-linking provides a method of stiffening the cornea to prevent progression of ectatic disease. This procedure, however, requires the surgical debridement of the corneal epithelium, saturation of the cornea with riboflavin ophthalmic solution, and illumination with ultra-violet A (365 nm) radiation. Side effects of surgical epithelial debridement include prolonged pain, epithelial healing, and vision recovery. In contrast, the procedure described in this application will not require epithelial debridement, and has the potential to halt progression of the disease while reducing post-procedure pain, and promoting faster vision recovery to baseline CDVA.

2.1 DESCRIPTION OF INDICATION FOR USE

The indications for use during this study will be the treatment of asymmetric corneas diagnosed with one of the following conditions: keratoconus, forme fruste keratoconus, post-LASIK ectasia, pellucid marginal degeneration, forme fruste pellucid marginal degeneration, diurnal fluctuation post-radial keratotomy, or Terrien’s marginal degeneration.

2.2 CURRENT TREATMENT AND LIMITATIONS

There is currently no medical therapy in the United States that preserves the corneal epithelium for the treatment of corneal ectasia associated with keratoconus, forme fruste keratoconus, post-LASIK ectasia, pellucid marginal degeneration, forme fruste pellucid marginal degeneration, diurnal fluctuation post-radial keratotomy, or Terrien's marginal degeneration. As a result, subjects who progress to severe disease must have more invasive procedures involving surgical removal of the epithelium, implantation of corneal rings, or penetrating keratoplasty.

3.0 STUDY DESIGN

3.1 OBJECTIVE

The objective of this study is to assess changes in visual acuity after corneal collagen cross-linking of asymmetric corneas.

3.2 DESCRIPTION OF THE STUDY

Approximately 3,000 eligible subjects presenting with asymmetric corneas will be enrolled at 21 clinical sites.

The primary effectiveness analysis will be based on 6-month post-procedure assessments. Subjects will be assessed post-procedure day 1, at 3 months and at 6 months. Visual acuity measurements and full ocular assessments (manifest refraction with CDVA, UCVA, slit lamp biomicroscopy including a rating of corneal haze, pachymetry, Pentacam corneal tomography, IOP) will be performed during that period.

Optional 1 week, 1-2 month, 12-month, 24-month, and 36-month assessments will also be performed, at the discretion of the physician. The 1-2 month visit may occur if the subject experiences changes in refractive error, and requires a new prescription for spectacles or contact lenses.

Optional assessments including corneal wavefront measurement, optical coherence tomography (OCT), Brillouin microscopy, iTrace wavefront aberrometry/topography, Orbscan corneal topography, or other non-invasive diagnostic tests that may be available to an investigator, as well as quality of life and/or comfort survey questions may be performed during the study period.

3.3 OUTCOME MEASURES

Effectiveness Outcome Measures

The following will be evaluated 6 months after the cross-linking procedure:

Primary effectiveness measure:
Change in CDVA

Secondary effectiveness measures:

Change in UCVA

Change in K_{\max}

Safety Outcome Measures

Safety will be evaluated by assessing the following:

Adverse events (AEs)

Serious adverse events (SAEs)

3.4 STUDY POPULATION

Up to 3,000 subjects with asymmetric corneas will be enrolled. After providing informed consent and documenting it in writing, subjects with keratoconus, forme fruste keratoconus, post-LASIK ectasia, pellucid marginal degeneration, forme fruste pellucid marginal degeneration, diurnal fluctuation after RK, or Terrien's marginal degeneration will be screened for participation in the study. Screening evaluations may be performed at any time within 3 months preceding or on Day 0, and subjects must fulfill the following criteria:

Inclusion Criteria:

1. Diagnosis of keratoconus, forme fruste keratoconus, post-LASIK ectasia, pellucid marginal degeneration, forme fruste pellucid marginal degeneration, history of radial keratotomy with fluctuating vision, or Terrien's marginal degeneration.
2. Must have provided informed consent, documented it in writing, and have been given a copy of the signed informed consent form.
3. Must be willing and able to return for scheduled treatment and follow-up examinations for the duration of the study.
4. Must be at least 8 years of age.

Exclusion Criteria:

1. Corneal thickness < 375 microns measured by ultrasound or Pentacam.
2. Contraindications or sensitivities to any study medications or their components.
3. Pregnancy or breastfeeding.
4. Any history of herpes simplex corneal disease in an eye to be treated.
5. Nystagmus or any other condition that would, in the judgement of the investigator, prevent a steady gaze during the treatment.
6. Inability to cooperate with diagnostic tests.
7. Enrollment in another ophthalmic clinical trial.

Randomization:

Randomization will be stratified by indication and by investigational site, with study subjects randomly assigned to one of three treatment groups. The three treatment groups consist of CXLO Corneal Strengthening Solution combined with one of 3 different UVA exposure parameters. The UVA treatment parameters will consist of:

- Group 1: 4 mW/cm² cycled On/Off automatically at 15 second intervals for 20 minutes (total UVA corneal surface dose of 2.4 J/cm²),
- Group 2: 6 mW/cm² cycled On/Off automatically at 15 second intervals for 20 minutes (total UVA corneal surface dose of 3.6 J/cm²), and
- Group 3: 4 mW/cm² cycled On/Off automatically at 15 second intervals for 30 minutes (total UVA corneal surface dose of 3.6 J/cm²).

4.0 STUDY TREATMENTS

4.1 INVESTIGATIONAL TREATMENT

One or both eligible eyes may be enrolled and procedure performed on the same day or on different days. Subjects eligible for enrollment will be instructed to instill Polytrim (or Floraquinolone or other appropriate broad spectrum antibiotic if the subject is hypersensitive) 4 times daily into the eligible eye(s) one day prior to treatment

- A. Instill anesthetic eye drops.
- B. Place a lid speculum in each eye undergoing treatment.
- C. Use a sterile ophthalmic sponge hydrated with saline or anesthetic drops to gently swab the surface of the cornea to remove mucus and any other debris and to enhance riboflavin penetration into the cornea. The epithelium is not to be removed, as treatment with an intact epithelium has the potential to halt progression of the disease while reducing post-procedure pain, complications related to epithelial debridement, and promoting faster vision recovery to baseline CDVA.
- D. Apply a sterile corneal sponge protector to the surface of the cornea to serve as a reservoir for CXLO Corneal Strengthening Solution.
- E. Saturate the sponge protector with several drops of CXLO Corneal Strengthening Solution. Thereafter, to assure for continuous application of CXLO solution to the surface of the cornea, keep the sponge moistened by applying 1-2 drops of CXLO solution every 1-3 minutes for 10-90 minutes (this range is required as different corneas load at different rates and the surgeon will visually confirm sufficient stromal loading later in the procedure).
- F. After 10-20 minutes of saturation, remove the lid speculum. Examine the eye using a slit lamp or slit light to confirm adequate saturation of the cornea, referencing the “flip-chart” of slit-lamp images, a copy of which is provided in Appendix 1. If the cornea is not adequately saturated, repeat the CXLO Corneal Strengthening Solution application instructions above,

and re-assess corneal saturation via slit-lamp or slit light examination every 5-10 minutes until adequate corneal stromal saturation is confirmed.

- G. After confirming adequate stromal saturation, irrigate the corneal epithelium with artificial tears for approximately 30 seconds prior to UVA illumination to avoid the “sunscreen” effect of riboflavin in the epithelium.
- H. Place the lid speculum(s) prior to UVA light application.

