5.0 STUDY PROCEDURES

5.1 INFORMED CONSENT

Prior to recruitment of any subjects into the study, written approval of the protocol, and informed consent and assent forms, must be obtained from the Institutional Review Board (IRB) for each participating clinical site.

Informed consent and assent forms, the assent form being applicable to subjects less than 18 years old, must be obtained and documented in writing prior to the initiation of any study procedures. The subject (or the subject's legally authorized representative) and the minor (when applicable) must be allowed sufficient time to thoroughly read (or have explained) the respective consent/assent form, which will be written at a level that can be understood by someone with minimal education.

The Investigator or his/her designee should answer any questions that the subject/representative might have. If the adult subject/parent/guardian and the minor, when applicable, agree to participate in the study, i.e., provides informed consent and assent, the subject/representative must sign both copies of the informed consent/assent forms. The witness and the Investigator must also sign both copies of these forms. One copy of these forms will be given to the subject/representative. If applicable, it will be provided in a certified translation of the local language.

Subjects who provide informed consent (and assent, if applicable) and document this in writing will be screened for eligibility. Screened subjects will be recorded on site-specific screening logs and once they are determined as being eligible, they will be enrolled into the study.

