6.0 SAFETY PARAMETERS

Safety assessments include adverse events/serious adverse events, visual acuity loss, slit lamp findings, and intraocular pressure. The reporting time period is from the day cross-linking is performed through the last through the last study visit.

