6.1 DEFINITIONS OF ADVERSE EVENTS

An adverse event is any untoward and unintended sign, symptom or disease temporally associated with the use of an investigational drug or device, or other protocol-imposed intervention, regardless of the suspected cause. Conditions or diseases that are chronic but stable should not be recorded on AE pages of the CRF. Changes in a chronic condition of disease that are consistent with natural disease progression are NOT adverse events and also should not be recorded on the AE pages of the CRF.

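### Adverse event reporting opens on the procedure day, one day after the protocol's own antibiotic starts, so reactions with onset before that day are not collected

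*Protocol*

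**What the plan says.** Protocol 4.1 opens with a pre-procedure medication: "Subjects eligible for enrollment will be instructed to instill Polytrim" (or a substitute antibiotic for a hypersensitive subject), to be used "4 times daily into the eligible eye(s) one day prior to treatment".

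Protocol 6.0 fixes when events are collected, for both adverse and serious adverse events: "The reporting time period is from the day cross-linking is performed through the last through the last study visit". Protocol 6.1 fixes what counts. An adverse event is one associated in time with the investigational product "or other protocol-imposed intervention, regardless of the suspected cause". Protocol 6.2 says that subjects exposed to the study treatment are evaluated for events, and that everything found is recorded whether or not it is attributed to treatment. Protocol 6.2.3 rates relatedness to the cross-linking procedure only.

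SAP 6.1.3 counts an event as treatment-emergent if it began on or after the first procedure date, or if the start date is absent and the event is not known to have stopped before that date. The SAP safety set contains treated subjects only, whereas Protocol 8.0 puts all enrolled subjects in the safety analysis.

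On screening, Protocol 3.4 states: "Screening evaluations may be performed at any time within 3 months preceding or on Day 0". Protocol 5.1 says of consent that it "must be obtained and documented in writing prior to the initiation of any study procedures", and of screened subjects that "once they are determined as being eligible, they will be enrolled into the study".

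**The concern.** The protocol gives subjects a drug because they are in the trial, counts reactions to it as adverse events, and then starts collecting events a day too late to see the earliest ones. An acute reaction to an eye drop can begin on the day of first use. A subject who reacts badly enough to be withheld from the procedure leaves no adverse event record under the stated rules. At stake is a complete account of harm from an exposure that the trial itself imposes. No effect on the visual acuity or K_max results is claimed.

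A second and smaller matter concerns the same drops. They are for subjects already judged eligible, yet eligibility may first be established on Day 0, when the day before has passed.

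**Working it through.** There is no stated figure to reproduce. The check is a comparison of timing rules.

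**Inputs.** Antibiotic use: the day before treatment (4.1). Start of reporting: the cross-linking day (6.0). Screening: from 3 months before Day 0 up to and including Day 0 (3.4). The protocol does not define Day 0. I take it as the procedure day, because the schedule of assessments calls the next day Post-Op Day 1.

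**Gap in the window.** Start of reporting minus antibiotic day = Day 0 − Day −1 = 1 day. With about 3,000 subjects each taking the drops once before a first procedure, the exposure outside the window is at most 3,000 × 1 = 3,000 subject-days. That bounds unobserved exposure, not the number of reactions.

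**Where a reaction to the drops would end up:**

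| Onset of the reaction | Protocol 6.0 and 6.2 | SAP 6.1.3 and Appendix C |
|---|---|---|
| Day −1, full date known, subject then treated | Before the period opens | Not treatment-emergent |
| Day −1, subject never treated | Period never opens; no exposure to study treatment | Not in the safety set |
| Day −1, day of onset left blank, same month as the procedure | Before the period opens | If entered, onset is set to the procedure date, so it is counted |
| Day 0 or later | Recorded, whatever the cause | Treatment-emergent |
| Day before a later second-eye procedure, first eye still in follow-up | Inside the period already open | Treatment-emergent, attributed to the last treatment received |

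The first two rows are the loss. The third shows that the SAP could handle the same reaction in opposite ways depending on how completely its date was written.

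**Day 0 screening.** Lead time needed for the drops: 1 day. Minimum lead time from screening: 0 days. Since 0 < 1, a subject first found eligible on the procedure day cannot have been instructed, as an eligible subject, to use drops the day before. A subject screened at least one day earlier can satisfy both sections.

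**The case against.** Four objections deserve weight.

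*Definition and window are different things.* Section 6.1 says what an event is and 6.0 says when events are reported, and the treatment-based frame is used consistently in 6.2 and in the SAP. This is correct: the two sections are not formally contradictory. But a definition that reaches every intervention imposed by the protocol does no work for the one intervention that always precedes the window. Aligning the two improves a stated rule.

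*Most reactions are caught.* A reader might infer that reactions to the antibiotic go uncollected altogether. The documents do not support that. Everything from the procedure day on is recorded regardless of cause. An antibiotic is also instilled after the procedure and may be continued for up to a week (4.1, step L), so many reactions would begin inside the window.

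*Hypersensitivity is already handled.* A reader might infer that the hypersensitivity mentioned in 4.1 is the event being missed. That wording concerns subjects known to be hypersensitive, who receive a substitute, and 3.4 excludes sensitivity to study medications. Only a new reaction with onset on the day before is lost.

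*Study treatment might include the drops.* They appear under the Study Treatments heading, so 6.2 could be read as covering anyone who took them. Even on that reading, 6.0 still opens on the cross-linking day.

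On Day 0 screening, a reader might infer that drops will be given before consent. Sections 3.4 and 5.1 both put consent first, so the text supports only an unresolved conflict. Nor is it telling that the Protocol Summary omits the drops from its procedure steps: those steps are headed as the day of cross-linking. Randomization stratified by site also argues against any claim that differing site practice biases the comparison of groups.

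**Conclusion.** The point holds within narrow limits. Reactions to the pre-procedure antibiotic with recorded onset before the procedure day, including those in subjects who react and are never treated, are not collected. The gap is one day per subject before the first procedure. Its yield in events is unknown, because the documents give no reaction rate. It is a modest safety-reporting defect that is cheap to close.

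The Day 0 conflict is real but minor. It touches only subjects first found eligible on the procedure day, a share that the documents do not give.

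Assumptions: Day 0 is the procedure day; the drops are used on the single day before it; and these sections stand unchanged in the protocol version 4.3 that the SAP cites, since the text available carries a revision history only to 04.2.

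**What to change.** 1. In Protocol 6.0, begin the reporting period at the first dose of the pre-procedure medication that the protocol imposes. Do not tie it to the first study procedure: screening examinations may take place up to 3 months before Day 0, and that wording would lengthen the period by as much.
2. In Protocol 6.2, extend evaluation to every subject who has taken that medication, treated or not.
3. In the SAP, keep the treatment-emergent definition and add one listing of events with onset between the first dose and the procedure. It should cover everyone who took the medication, because the present safety set contains treated subjects only. State how a partly dated onset is assigned between this listing and the treatment-emergent tables.
4. Separately, the sponsor should reconcile Protocol 3.4, 4.1 and 5.1 for subjects first found eligible on the procedure day. How that is settled is a clinical matter, and no rule is proposed here.

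Cost: about one more day of reporting per subject, a few untreated subjects with events to record, one listing, and small wording changes in both documents. The adverse event form already captures date of onset, and Protocol 5.3 already has prescription drugs recorded on the CRF.
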